At entry, we will record demographic information (age, gender, ethnicity, family income, parental education, past medical history), height, weight, blood pressure, blood test results (C3, albumin, cholesterol, creatinine), urine protein values by dipstick (routine clinical practice is to use urine albumin dipsticks [Albustix™, Bayer], but urine protein to creatinine ratio will be recorded if available), medical history and details of steroid prescription. For patients entering at first or second relapse, demographic and treatment information regarding first presentation and/or first relapse will be collected using retrospective chart review when available. We will allow for enrollment up to second relapse (lengthening time interval to obtain consent) in order to maximize patient recruitment. Standardized assessments by physicians will be performed at the following study points: study entry, semi-annual study visits, and at study end.

Data for study points will be obtained using one or all of the following methods: chart review, reviewing patient log books of daily home urine protein measurements and steroid dose given, and phone calls to family to confirm details of clinical course (including date of proteinuria remission for each relapse). Logs maintained by patients are part of routine clinical care in nephrotic syndrome; all study patients will be provided with standardized log books for medications and relapse tracking. This schedule and method of assessments for study points were designed to mirror routine clinical care (as reported by most sites) and to maximize feasibility while maintaining ongoing engagement by study patients and physicians.

Defining an episode of treatment: As nephrotic syndrome is a relapsing and remitting disease, a significant portion of the study data will involve documenting treatment for both first presentation and

relapses of nephrotic syndrome (called ‘episodes’ in this study). Detailed steroid prescription information will be recorded at entry, and at the beginning and end of all subsequent episodes.

An **episode** is defined as the time from start of full dose steroid therapy (60 mg/m² or 2mg/kg) to cessation of steroids or re-start of full dose steroids as in steroid dependent patients who relapse while tapering steroids.

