The standard definitions used in nephrotic syndrome are provided in Appendix, Table 2. The data collection forms, shown in Appendix Figure 3, are designed to capture steroid prescriptions for each episode from the date of start of full dose steroid therapy (60 mg/m² or 2mg/kg) to cessation of steroid therapy or restart of full dose therapy. Each patient’s steroid prescription for an episode will be linked to the prescribing physician.

Data quality and standardization: Standardized case report forms will be used for data collection regarding the clinical course, outcomes and treatments for childhood nephrotic syndrome. All patient and physician data will be entered by study staff into a multi-centre online database (REDCap™, a web-application which allows users to build databases securely for the purposes of research and in particular for longitudinal cohort studies, <http://project-redcap.org/> hosted by Women and Children’s Research Institute, Edmonton, see letter from [name]). Data are being monitored weekly to address data quality issues in real-time. Based on the 77 subjects enrolled to date, we have confirmed that the majority of data to be collected for this study is recorded routinely by nursing staff in clinical care, and the web based system does not pose significant additional onerous data entry requirements.

The study will be coordinated centrally in Calgary. Two central study staff (study nurse and data analyst) will train all other site-specific study staff regarding study goals and objectives, data management and data entry. We put in place several measures to ensure data consistency and standardization including: piloting case report forms and standardizing forms; training site staff for data element definitions; using a data dictionary; establishing inter-rater reliability for data entry using two study staff at each site at start of study; and pre-study patient visit planning to standardize data collection and entry. Every 3 months, data analyst will review data entry completeness for individual patients and send reminders to appropriate site investigators for data completion. There will be a 2 step review for data completeness for each patient record – first by the data analyst and second by a lead investigator or designate. Data are time-stamped as complete after review. Key measures of data quality were identified a priori; a sample data quality report is attached in Appendix, Tables 3 and page 16.

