Design: To determine the associations between centre-, physician-, patient-level characteristics and i) steroid dose prescribed, and ii) length of steroid treatment for first presentation and subsequent relapses of nephrotic syndrome, and to identify reasons for practice variation between and among pediatric nephrology care providers and centres, we will use a mixed methods approach as defined by Creswell & Plano Clark.⁵⁶ The primary study is a quantitative study using the prospective cohort as described. A qualitative study, serving a supplementary role, is embedded within the larger quantitative study to provide a deeper understanding of the complex multi-level processes that lead to practice variation between centres and between physicians within centres. True to qualitative approaches, no a priori hypothesis is specified for this aim. At the completion of quantitative and qualitative studies, we will use a convergent parallel mixed methods analytic approach (both quantitative and qualitative data collected and analysed during the same phase of research, then two sets of results are merged for an overall interpretation), to compare qualitative and quantitative data across centre-, physician- and patient-level attributes. The results of both components will inform the ‘greater whole’ - a comprehensive understanding of why there is variability in care for nephrotic syndrome – a key step to overcoming barriers to implementation of best practice approaches for treatment of nephrotic syndrome across Canada and to make future randomized controlled trials more feasible.

Description of the quantitative study: We will use the prospective cohort described in section 3.1 to determine the associations between centre-, physician-, patient-level characteristics and outcomes. All patients with steroid sensitive nephrotic syndrome and all physicians enrolled into the prospective cohort will be eligible for this study. We will use the hierarchical data in the prospective cohort. The observation period for this objective will be a maximum of 4.0 years and minimum of 6 months.

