Outcomes: The primary outcome is steroid prescribed per episode. We will examine: a) total dose patients receive for an episode; and b) average daily dose by dividing the total dose by duration (in days) of the episode. Dose will always be in mg/m² prednisone equivalents. This outcome definition is consistent with measures of steroid exposure used in prior nephrotic syndrome steroid dosing studies.^{38,55} We are evaluating steroid prescription per episode because in this objective, we will study determinants of variability in steroid prescription for episodes of proteinuria rather than patient outcomes related to cumulative exposure of steroids (e.g. relapse rate). All episodes will be categorized either as first presentation or relapse. The secondary outcome will be length of episode in days.

Exposures: Exposure variables of interest are categorized into centre-, physician- and patient-level variables. Centre-level variable is defined as existence of a standardized protocol within centre for treating first presentation and relapses (information will be obtained from the site investigator as existence of centre based protocols [yes/no]). Physician-level variables are gender, year of graduation from nephrology fellowship, and location of nephrology training (Canada vs. outside Canada). These centre- and physician-level variables were shown to impact variability in practice patterns according to our published survey.²² Patient-level variables are age, gender, ethnicity, and status at entry into study (first presentation, relapse). These variables are further described in Appendix, Table 5.

Analysis plan: We will describe the primary and secondary outcomes according to each of centre-, physician- and patient-level characteristics with 95% confidence intervals. To study the associations of centre-, physician-, patient-level characteristics with the primary outcome (steroid prescribed per episode), we will use mixed effects models with fixed effects for centre (standardized protocols yes/no), physician (gender, years in practice, location of training), and patient (age, gender, ethnicity) characteristics and random effects to account for physicians clustering within centre, patients clustering

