within physician, and episodes clustering within patients. We will create separate models to examine both total dose patients receive for the episode, and average daily dose by dividing the total dose by duration (in days) of the episode. The unit of analysis will be the episode. Each episode will be categorized as either first episode or relapse at the patient level in the same model. The same methodology will be used to study the length of episode in days (secondary outcome).

Description of the embedded qualitative study: The embedded qualitative study will enrich the quantitative results by providing detail regarding attitudes, beliefs and local factors driving variation in care - fundamental to understanding the complexity of health care professional decision-making.^{57,58} Theoretically grounded in the *Ottawa Model of Research Use*,⁵⁹ we are conducting focus groups with health professionals who care for children with nephrotic syndrome to probe the reasons for variation in steroid protocols ('why do people do what they do'). Ten focus groups, one per site with 6-8 participants per group and each lasting 60 minutes, are planned. Informed consent will be obtained and participant responses will be anonymized. We are not requesting funds from CIHR for this study as we have completed 8 of these 10 focus groups; however, we have provided the interview guide and the preliminary results in the Appendix (pages 22-24) - as it is a critical component of our mixed methods design and KT plan.

Integration of quantitative and qualitative studies: We will independently analyze the qualitative and quantitative data using analyses for Objective 2 as detailed above. We will use a convergent mixed methods analytic approach to compare the results obtained in the quantitative with qualitative components (Appendix Figure 6), using matrices of the hierarchies of centre-, physician- and patient-levels and explanatory quantitative variables at each level and themes related to these same levels arising from the qualitative study (e.g., existence of standardized protocols in each centre, age and training background of the physician, patient's age and ethnicity; Appendix Table 6), asking whether two types of data are congruent or not.

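### Objective 2 models treat a steroid course cut short by a relapse on taper as a completed course, so prescribing effects are mixed with relapse risk

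*Protocol*

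**What the plan says.** Protocol section 3.1 (Defining an episode of treatment) starts an episode at full-dose steroids and ends it at one of two events: "to cessation of steroids or re-start of full dose steroids as in steroid dependent patients who relapse while tapering steroids". The data collection forms follow the same rule, capturing prescriptions "to cessation of steroid therapy or restart of full dose therapy", and each patient's "steroid prescription for an episode will be linked to the prescribing physician".

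Section 3.3 builds Objective 2 on that unit. The design concerns steroid dose and "length of steroid treatment for first presentation and subsequent relapses of nephrotic syndrome". The primary outcome is examined as "total dose patients receive for an episode" and as that total divided by the episode's days; the secondary outcome is episode length. The reason given for working per episode is that "we will study determinants of variability in steroid prescription for episodes of proteinuria rather than patient outcomes related to cumulative exposure".

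The models have fixed effects for centre protocol (yes/no), three physician characteristics and three patient characteristics, with random effects for physicians in centres, patients in physicians and episodes in patients. The only episode-level marker is this: "Each episode will be categorized as either first episode or relapse at the patient level in the same model". The analysis of length adopts the same modelling approach. On data capture, section 3.1 states: "Detailed steroid prescription information will be recorded at entry, and at the beginning and end of all subsequent episodes".

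**The concern.** First episode or relapse describes how an episode began, not how it ended. An episode that ran its planned taper and one stopped by a relapse on taper enter the model as the same kind of observation. In the second kind, the child's disease set the length and total dose as well as the prescriber. Because what is lost is the lower-dose tail, the average daily dose usually rises.

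A patient random effect absorbs a stable tendency of the patient. It does not restore the missing part of a particular course.

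The consequence bears on the stated aim. Two centres with an identical planned course but different on-taper relapse risk would show different lengths and average doses. Two centres with different planned lengths would usually show too small a difference. The protocol intends to use these results to judge which physician and centre factors drive variation and to shape implementation (sections 2.8 and 6.0).

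**Working it through.** **1. Do the stated model terms mark the end of an episode?** Section 3.3 counts 8 explanatory variables. The named ones are 1 centre + 3 physician + 3 patient = 7, and episode type (or status at entry) makes 8. None marks how the episode ended, and no censoring rule is given for length. The protocol's upper count of episodes reproduces: 597 × 1.70 = 1014.9, stated as 1015. It has no figure for the share ended by restart.

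**2. One course cut short.** Take the 6 + 6 week regimen of section 2.3 (84 days) at the 60 mg/m² full dose of section 3.1. The alternate-day dose is not given; assume 20, 40 or 60 mg/m². A restart on day 63 gives:

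- length 63 instead of 84 days (−25%)
- total dose 2,740 vs 2,940, 2,960 vs 3,360, or 3,180 vs 3,780 mg/m² (−7% to −16%)
- average daily dose 43.5 vs 35.0, 47.0 vs 40.0, or 50.5 vs 45.0 mg/m² (+24% to +12%)

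**3. Effect on differences between regimens.** Let D be daily weeks, T taper weeks and h the on-taper hazard per week (annual rate/52), constant during taper. Then

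- share cut short = 1 − exp(−hT)
- mean recorded length = D + (1 − exp(−hT))/h

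The 4+4 and 6+6 regimens are from section 2.3. The 6+10 and 6+20 splits are assumed, to match the survey median of 16 and maximum of 26 weeks in section 2.4. Annual hazards of 0.5, 1.68 and 3.36 are assumed; 1.68 is the overall relapse rate in section 3.2, not an on-taper rate. Scenario A uses the same hazard for all regimens. Scenario B halves it in the longer taper, since sections 2.3 and 2.6 report conflicting evidence on whether longer courses reduce relapse.

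| Comparison (true gap) | A: recorded gap, weeks | A: kept | B: recorded gap, weeks | B: kept |
|---|---|---|---|---|
| 8 vs 12 weeks (4) | 3.91 / 3.70 / 3.45 | 98 / 93 / 86% | 3.99 / 3.97 / 3.93 | 100 / 99 / 98% |
| 12 vs 16 weeks (4) | 3.70 / 3.09 / 2.39 | 93 / 77 / 60% | 3.93 / 3.78 / 3.57 | 98 / 95 / 89% |
| 12 vs 26 weeks (14) | 12.36 / 9.28 / 6.25 | 88 / 66 / 45% | 13.24 / 11.64 / 9.76 | 95 / 83 / 70% |

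Longer tapers are cut more often unless their hazard is below T_short/T_long times that of the shorter taper: 4/6 = 0.67, 6/10 = 0.60, 6/20 = 0.30.

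**4. Average daily dose.** This is E[(60D + 20t)/(D + t)] with t = min(relapse time, T) and an assumed 20 mg/m² per day on taper. The true 12 vs 26-week gap of 10.8 becomes 9.7 / 7.5 / 5.4 in A and 10.4 / 9.7 / 8.8 in B. The true 8 vs 12-week gap of 0 becomes +0.1 / +0.5 / +0.8 in A and −0.1 / −0.2 / −0.4 in B. The direction is not general.

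**5. Same plan, different relapse risk.** With the same formulas and a 26-week plan in both centres, hazards of 0.84 and 1.68 per year give recorded means of 23.1 and 20.7 weeks and average daily doses of 31.7 and 33.9 mg/m². With a 12-week plan the means are 11.7 and 11.5 weeks.

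**6. Check of the remedy.** Take half 12-week and half 26-week courses, true mean 19.0 weeks, with no study-end censoring. With restarts censored, S(12) = e26/(e12 + e26), where e = exp(−6h) with each regimen's own h, and the Kaplan-Meier mean is 12 + 14 × S(12).

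| Mean, weeks | A | B |
|---|---|---|
| As recorded | 18.0 / 16.1 / 14.1 | 18.5 / 17.3 / 15.9 |
| Restarts right-censored | 19.0 / 19.0 / 19.0 | 19.1 / 19.3 / 19.7 |
| Restart-ended episodes dropped | 18.5 / 17.4 / 16.0 | 18.9 / 18.6 / 18.1 |

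Dropping episodes favours short courses. At 1.68 per year 82% of 12-week courses remain, but only 52% of 26-week courses (72% with the hazard halved).

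**The case against.** The strongest reply is that the target is coherent as written. Objective 2 names dose received and realised length, and a full-dose restart does end one prescription and begin another. Calling the earlier course truncated substitutes the planned course for the received one. The data survive, since each full-dose start is a dated study point, and a flag or sensitivity analysis could sit in an analysis plan that is not shown.

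Much of this stands. Received dose and realised length are legitimate outcomes, and the restart is rightly kept as a separate episode. A reader might infer that the episode rule is wrong; the protocol does not support that. What remains is that the method for length is stated, it counts an interrupted course as complete, and the stated purpose is prescription as distinct from patient outcomes.

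Three other stronger readings also fail.

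- **Up to half of episodes affected.** The figure of up to 50% in section 2.2 counts children who relapse, pools frequent relapsers with steroid-dependent children, and includes relapse after cessation, which truncates nothing.
- **End type belongs in the model as a covariate.** It arises after the prescription and may depend on it. The count of 8 variables does not rule out further terms either; it only supports a rule of thumb on observations per variable.
- **The two end definitions contradict each other.** Section 3.1 sets a data-collection point for the end of a relapse (remission and off steroids) and, separately, a treatment interval that can end at a restart. A child restarted on taper meets only the second, but the restart is dated elsewhere in the same list. This calls for clearer wording only.

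**Conclusion.** The point holds as an improvement worth making, not as an error in the episode definition. As specified, the Objective 2 models mix prescribing with relapse on taper. Differences in length and total dose are usually attenuated; for average daily dose the direction varies.

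The size cannot be derived from the protocol. The illustrations rest on an assumed constant on-taper hazard, assumed splits for the 16- and 26-week courses and an assumed taper dose. Under them the 8- and 12-week regimens described in section 2.3 are little affected, and the concern is mainly with long tapers. The 26-week figure is a survey maximum for first presentation only. How far any centre or physician coefficient would move depends on how closely that factor tracks planned course length, which is not given. Confidence is moderate.

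**What to change.** Keep the episode rule and the received-dose and realised-length outcomes. Then:

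1. Derive for each episode whether it ended by cessation, full-dose restart or study end, from data already collected. Do not enter this as a covariate.
2. Beside the realised-length model, report a length analysis with episodes ended by restart or study end right-censored, stating that censoring is assumed independent given the covariates.
3. Where the prescription recorded at episode start holds the planned course, model planned length, total dose and average daily dose beside the received values.
4. Repeat the received-dose models without restart-ended episodes as a sensitivity analysis only. Do not censor on the dose scale: dose accrues at different rates, so such censoring is informative.
5. Reconcile the wording of the end-of-relapse data point and the episode end in section 3.1 for a child restarted on full dose while tapering.

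The cost is one derived flag, a second set of models and a wording change. A small form change may be needed if the forms (in an appendix not shown) do not hold the planned taper. The downside is two sets of results to reconcile. The censored analysis is also somewhat biased if on-taper relapse depends on course length (up to 0.7 weeks in the check above), and possibly more if relapse-prone children are prescribed different courses, which the check does not model.

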2.4 Although a reasonable body of evidence is available to guide practice, practice variation is common in nephrotic syndrome. The available evidence base for treatment of first presentation and relapses of nephrotic syndrome were synthesized and published in several systematic reviews, local guidelines,^{2,40,41} and also in a recent international clinical practice guideline.⁴² Nevertheless, lack of consensus regarding best treatment approaches is a well-known international phenomenon. Variation in care was documented in surveys of American pediatric nephrologists in 2000 and 2009; however, little has been done to address this problem in the United States or elsewhere.^{20,21} We performed a similar survey which was sent to all Canadian pediatric nephrologists (n=58) and achieved a 69% response rate. The results showed significant variation in steroid protocols and also in the choice of steroid sparing drugs and biopsy practices (see manuscript attached, [name] S, *Pediatr Nephrol* 2013). The total duration of steroid therapy ranged from a minimum of 7.5 weeks to a maximum of 26 weeks (median 16 weeks) for first presentation of nephrotic syndrome – likely contributing to considerable variation in cumulative steroid exposure among patients who may otherwise have similar clinical presentations. Sample protocols used by Canadian physicians and centres are shown in Appendix Tables 1a and 1b. The overall impact of this variability in steroid exposure on relapse rates of Canadian children with nephrotic syndrome has not been formally assessed and remains the most important and compelling unanswered question.

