Patient enrollment: Two team members from each participating site will be primary contacts for the study (one physician and one nurse/research staff). Every 2 weeks these individuals will generate a list of patients seen with nephrotic syndrome by reviewing inpatient and outpatient data (clinic scheduling records) to determine eligibility. All patients with a clinical diagnosis of nephrotic syndrome who meet the inclusion and exclusion criteria will be introduced to the study by the primary treating physician. The site investigator will approach patient/parents to obtain informed consent and will also obtain assent from older patients (age >12 years). Patients will be enrolled in the study if they meet inclusion criteria and

their legal guardian has given informed consent. Consent forms will be available in English and French. Logs of all patients screened and consented, and for those who declined the reason will be kept.

Physician enrollment: Informed consent will be obtained from physicians within participating nephrology care teams to allow their demographic information (age, gender, location of nephrology training, years in practice) to be collected. Physician data will be linked to their patient's data in the nested data architecture. Once linked, physician identifying information will be removed. If a consenting patient's physician declines to participate in the study, the patient's data will be linked to a generic category of 'unknown physician.'

Patient data being collected: Study data will be collected at the following study points (see Figure below and more details shown in Appendix, Figure 2): 1) study entry (whether first presentation, first relapse or second relapse); 2) at the beginning of all subsequent relapses [defined as proteinuria > 3+ on dipstick, > 3g/L on urinalysis or urine protein to creatinine ratio > 200 mg/mmol for 3 consecutive days or start of full dose steroids (60 mg/m² or 2mg/kg)]; 3) at the end of first presentation and end of all subsequent relapses [defined as both remission of proteinuria – negative or <1.0 g/L protein on dipstick for 3 consecutive days, and off steroids]; 4) study visits every 6 months after entry; 5) at start of all steroid sparing agents; 6) at time all kidney biopsies; and 7) study end.

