Privacy and confidentiality: We will assign unique study numbers to patients, physicians and centres – to protect anonymity of all participants and centres. All identifying information will be securely stored at individual sites and will not be shared with central study staff.

Characterizing the cohort: We will describe (using means with standard deviation, medians with interquartile range and proportions as appropriate) the cohort demographics, and all outcomes of interest by centre-, physician, and patient- level variables. We will describe the following outcomes: overall steroid prescribed (total dose and number of treatment days), time to first relapse, relapse rate during observation, time to steroid sparing agents, choices of steroid sparing agents and indication, time to kidney biopsy, reasons for biopsy, complications of steroid therapy. Outcomes related to complications of steroid treatment will include: anthropometric changes during observation period (age- and sex-specific standard-deviation scores (z scores) for height, weight, and body-mass index); persistent systolic/diastolic blood pressure $\geq 95^{\text{th}}$ percentile during observation period [yes/no] and requirement for antihypertensive therapy [yes/no] and duration of therapy; and external manifestations of steroid toxicity evident during semi-annual study visits (Cushingoid faces [yes/no], hypertrichosis [yes/no], cataracts [yes/no], striae [yes/no], acne [yes/no]). Definitions of external manifestations of steroid toxicity are

similar to those observed in prior nephrotic syndrome steroid dosing studies.³⁸ See Appendix, Table 4 for detailed description of these variables.

3.2 Work plan for objective 1

Design: To determine the association of steroid dose prescribed with relapse rates, we will use the prospective cohort as described in section 3.1. We hypothesize that increasing steroid dose prescribed per unit time will be associated with decreasing relapse rates. All patients with steroid sensitive nephrotic syndrome enrolled into the prospective cohort will be eligible for this study. The observation period will span a maximum of 4 years and minimum of 6 months. Figure 4 in the Appendix provides a visual representation of the outcome and exposure as defined below for this objective.

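### External steroid-toxicity signs are scored at visits timed from entry, with no account of time since the last dose, so fading signs are more often missed after shorter courses than after the longest

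*Protocol*

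**What the plan says.** Section 3.1 (Characterizing the cohort) lists complications of steroid treatment among the outcomes to be described. One group is "external manifestations of steroid toxicity evident during semi-annual study visits", each scored yes or no: Cushingoid appearance, hypertrichosis, cataracts, striae and acne. The visits are "4) study visits every 6 months after entry", and entry is the start of a presentation or relapse. The same section states: "Standardized assessments by physicians will be performed at the following study points: study entry, semi-annual study visits, and at study end". The end of each episode is also a data-collection point, but it is not in that list.

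The other toxicity outcomes are defined differently. They include "anthropometric changes during observation period", persistent high blood pressure over the same period, and "requirement for antihypertensive therapy [yes/no] and duration of therapy".

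The plan is to describe "all outcomes of interest by centre-, physician, and patient- level variables". On course length, section 2.4 reports a survey of Canadian paediatric nephrologists with a range of 7.5 to 26 weeks, "median 16 weeks) for first presentation of nephrotic syndrome". Section 2.5 adds that duration was associated with physician seniority and with whether the centre has a standardized protocol.

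**The concern.** A sign that fades once steroids stop can be recorded only if the examination falls during a course or soon after it. The examination dates are fixed from entry, while the end of the course depends on the regimen. Regimens vary with the same physician and centre characteristics by which the outcomes will be tabulated. A table of external signs by centre would therefore mix two things: whether children developed the sign, and how recently they had been dosed when examined.

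Section 1.0 names minimizing treatment toxicity as a goal of care, and section 6.0 takes the cohort description to the meeting that will draft best-practice approaches. If fading signs are under-recorded, and more so after shorter courses, a reader of that table could overstate the difference in toxicity between short and long regimens.

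**Working it through.** The protocol states no figure for toxicity, so there is none to reproduce.

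**Inputs from the protocol.** Visits every 6 months = 365.25 / 2 / 7 = 26.09 weeks. First-presentation courses of 7.5, 16 and 26 weeks (section 2.4). Relapse rate 1.68 per person-year and average follow-up of 2 years, about four visits (section 3.2). Minimum follow-up of 6 months, about one visit (section 3.1).

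**Assumptions.** Persistence of a sign after stopping is not given, so 0 to 20 weeks is examined. Relapse-course length is not given in the text shown and is set equal to the entry course.

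**Step 1: relapse-free child at the first visit.** Weeks off steroids = 26.09 minus course length.

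- 7.5 weeks: 26.09 - 7.5 = 18.6
- 16 weeks: 26.09 - 16 = 10.1
- 26 weeks: 26.09 - 26 = 0.1

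A sign lasting under 10 weeks is seen only after the 26-week course. One lasting about 10 to 18 weeks is also seen after the 16-week course. One lasting 19 weeks or more is seen after all three.

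**Step 2: allow relapses, first visit, sign lasting 8 weeks.** The mean interval is 52.18 / 1.68 = 31.06 weeks. It is read either as time off steroids or as a full cycle, the latter leaving 31.06 - 16 = 15.06 weeks off. After a 16-week course the sign is visible at the first visit only if a relapse has started in the 10.09 weeks since stopping:

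- rate per off-steroid year: 1 - exp(-10.09 / 31.06) = 28%
- rate per calendar year: 1 - exp(-10.09 / 15.06) = 49%

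After a 26-week course it is 100%, because steroids stopped 0.1 weeks earlier. Simulation gives 38-46% after a 7.5-week course. Once relapses are allowed, detection at this visit is therefore not strictly ordered by course length. The clear contrast is with the longest course.

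**Step 3: four visits over two years, by simulation.** For the 8-week sign, the share of visits at which it is visible is set against the true share of time it is present:

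| Relapse rate read as | Course | Visible at visits | Truly present |
|---|---|---|---|
| per off-steroid year | 16 weeks | about 43% | 59% |
| per off-steroid year | 26 weeks | 68% | 69% |
| per calendar year | 16 weeks | 65% | 77% |
| per calendar year | 26 weeks | 98% | 97% |

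The visits understate the sign after 16-week courses by 12 to 16 points and are within about a point of the truth after 26-week courses.

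**Step 4: seen at one or more of four visits.** If a sign vanishes on stopping, 58-67% of children on 7.5-week courses would ever be recorded, against 92-100% on 26-week courses. At 20 weeks' persistence it is 100% for both.

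**The case against.** The strongest reply is that longer courses mean more steroid, so a higher visit prevalence at long-course centres is largely real. In the simulations the share of visits on steroids does broadly follow time on steroids. This stands in part: Step 3 shows that true exposure accounts for some of the gap but not all of it.

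Other points also stand:

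- The 7.5-26 week range consists of survey answers for first presentation. It is not a set of centre averages and does not cover relapse courses. Children may also enter at a first or second relapse.
- Most children relapse and are seen several times, so the relapse-free child at the first visit is the clearest case and not the typical one.
- The five signs need not fade alike, and the protocol does not say which do.
- Appendix Figures 2 and 3 and Table 4, which hold the schedule, forms and definitions, are not in the text supplied. Signs may already be recorded at the end of an episode.
- The schedule was deliberately set to follow routine care.

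A reader might infer that all steroid toxicity is captured only at six-monthly visits. The protocol does not support that: anthropometry, blood pressure and antihypertensive treatment are defined over the observation period or without reference to a visit, and standardized assessments also take place at entry and study end. A reader might also infer that what matters is whether the course is still running at the visit. The arithmetic does not support that either, since even the 26-week course has nominally just ended. Time since stopping is the relevant quantity.

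**Conclusion.** The point holds for external signs that fade after steroids stop, and only for those. Their recording depends on time since the last dose, which differs with course length, and the planned centre and physician descriptions do not separate this from occurrence. With an assumed 8-week persistence, detection at the first visit is 28-49% after a 16-week course against 100% after a 26-week course. That visit matters most for late entrants, who may have only one. The gap narrows over repeated visits and longer persistence, and the timing effect is essentially gone by about 19-20 weeks.

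These sizes rest on assumed persistence and on relapse courses as long as the entry course. It would go too far to say that centre differences in these signs would be artefact, because part is genuine exposure. The signs enter neither the Objective 1 nor the Objective 2 models, so those analyses are unaffected. This is a minor improvement to a descriptive outcome.

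**What to change.** 1. Report visit-based prevalence of the external signs overall and, alongside it, by steroid status and weeks since last dose at the visit. The prescription data already collected supply both. Keep the overall centre comparison. Steroid status at the visit is itself a consequence of course length, so comparing centres only within those strata would remove real differences. It would also be thin, at 597 / 13 = about 46 patients per centre.

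2. State which signs are expected to fade. For those, add a yes/no item for presence at any time since the last assessment at the six-monthly visit and, if the form does not already have it, at the existing end-of-episode point. Report this source separately from the standardized physician examination: chart or telephone reports are less standardized, and frequent relapsers have more chances to be recorded.

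The cost is a few form items and one extra table, with no new visit or procedure. The table can be added at any time, but signs not recorded when present cannot be recovered reliably later, so the form change should come first.
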